### Preliminary Studies:

[figure not shown]

Figure 2. Significant differences (\* indicates  $p < .010$ ) between healthy controls (HC) and PD groups according to swallowing safety (PA scores; panel A) and disease severity (Hoehn & Yahr scale; panel B).

of various intensities. Our study compared 14 patients with PD to 13 age and sex matched healthy adults (HCs). The results show that people

with PD exhibit blunted magnitude estimation of inspiratory resistive loads as compared with the control group regardless of whether they exhibit measurable decline in swallowing safety, or of disease severity (Figure 2 panels A and B). These data indicate general respiratory sensation is blunted even when dysphagia is not present, and in the early stages of the disease, thus lending preliminary support to the hypothesis that blunted respiratory somatosensation precedes the onset of swallowing deficits in PD.

*Reflex cough sensitivity is blunted in later PD compared to earlier PD and age-matched controls:* In an ongoing study we are measuring sensitivity to the airway irritant capsaicin by examining the perceived UtC. To date, participants include 76 men and women with PD, ranging from 1 to 23 years post-diagnosis and 51 age-matched control participants. Our interim analysis show that participants within 10 years of diagnosis (Figure 3, PD 1-4 and PD 5-9 groups) do not exhibit a significant difference in the UtC sensitivity as compared to the control group, however the PD 10+ group does exhibit a significantly blunted UtC sensitivity compared to controls (Figure 3).

*General respiratory sensation is blunted in PD, independent of disease severity or swallowing safety:* In order to understand whether people with PD experience blunted respiratory somatosensation we conducted a preliminary study to examine the perception and magnitude estimated of inspiratory loads

[figure not shown]

Figure 3. Urge to cough (UtC) sensitivity slope comparison between healthy controls (HC), and PD duration groups. PD1-4 is 1-4 years post PD diagnosis; PD5-9 is 5-9 years post PD diagnosis; PD 10+ is more than 10 years post PD diagnosis. \* is significantly different at  $p < .001$ .

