### Airway sensory processing in people with PD

Central neural processing of sensory stimuli is critical for generating appropriate motor plans, and this sensorimotor relationship is disrupted in PD, resulting in many of the hallmark motor symptoms (9-11). Sensory processing involves both discriminative and affective processing components, and each is critical for generating an appropriate motor response. Discriminative processing refers to the ability to detect and gauge the intensity or magnitude of a stimulus, whereas affective processing refers to determination of stimulus characteristics, such as pleasantness or unpleasantness (4, 18). As well, sensory stimuli may be gated, or filtered, out from connecting to the sensory cortex, and this process is normal and expected for many somatosensory modalities to prevent an over abundance of redundant sensory stimuli (19, 20). Our preliminary data suggest that there are changes in both discriminative and affective processing and filtering of airwaysensation in people with PD as compared to an age- and sex-matched control group (21), however to date it is unknown whether these deficits are related to observable motor deficits of swallowing or cough. The objective of this aim is to determine whether measures of discriminative and affective processing of general airway sensation is/are associated with deficits in reflex cough and swallowing function. Further we aim to determine whether over-filtering of airway stimuli is associated with swallowing or cough deficits. Based on preliminary data we expect that people with PD will exhibit reduced discriminative processing components of airway stimuli. With disease progression, measures of affective processing components will decline and this will directly correlate with diminished reflex cough sensitivity and swallowing function. In order to achieve this objective, we will measure swallowing and cough function, reflex cough sensitivity, and the event-related sensory evoked potential (SEP) to an airway stimulus. We will compare the latency and amplitude of the SEP waveform component peaks to swallowing safety and physiology, and cough effectiveness and sensitivity, in people with PD across a range of disease durations. The rationale is that by determining the relationship between discriminative and affective processing of airway sensation and airway protective behaviors (swallowing and cough) we will better understand what type of sensory deficits are impacting airway protective function.

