**Preliminary studies: Reduced**

|    | P1          |            | N1          |         | P2          |         | N2          |            |
|----|-------------|------------|-------------|---------|-------------|---------|-------------|------------|
|    | Mean (SD)   | P-value    | Mean (SD)   | P-value | Mean (SD)   | P-value | Mean (SD)   | P-value    |
| PD | 0.59 (0.41) | .05 | 0.70 (0.55) | 1.0     | 0.38 (0.35) | 0.69    | 0.27 (0.24) | .02 |
|    | 1.26 (0.91) |            | 0.62 (0.31) |         | 0.34 (0.30) |         | 0.88 (0.68) |            |

Table 4. Means and standard deviations (SD) for the airway SEP (Pitts et al., 2016)

*discriminative and affective processing of airway mechanical stimuli in PD:* We have recently reported the results of our study investigating the processing of an air-puff stimulus to the posterior pharyngeal wall in people with PD. Participants were 13 people with PD, and 7 age- and sex-matched healthy older adults (controls). In both the PD and control participants we were able to successfully record SEP component peaks (Figure 7). People with PD exhibit changes to

both P1 (discriminative) and N2 (affective) peaks as compared to healthy older adults (Table 4). Specifically, people with PD over-filter the P1 and N2 peaks, indicating that there is sensory information that is prohibited from reaching the level of conscious perception and processing. A limitation of this study was that the apparatus for delivering the air puff stimulus was uncomfortable for most participants, and this may have increased attention to the stimulus, which is known to modulate the N1, P2 and N2 peaks (33). Nonetheless, this preliminary study lends support our hypothesis that discriminative and affective processing and stimulus filtering are affected in PD, however it remains unknown whether/how attention affected these results, or whether they relate to changes in the airway protective functions of cough and/or swallowing.

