## 6. Research Plan:

### **Protocol 1 (Aims 1-3)**

This prospective experimental study will include male and female adults with PD, as well as a control group consisting of healthy adults. We aim to recruit 30 participants in each group. We will recruit PD participants from the patient population at UF Fixel Institute for Neurological Diseases. Healthy control participants will be recruited from the community population, including spouses and caregivers of PD participants, as well as HealthStreet. All participants will provide written consent before enrollment into the study, which will be approved by Institutional Review Board (IRB) at the University of Florida.

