## **Statistical Analysis**

**Aim 1:** A multiple regression analysis will be conducted with the slope magnitude estimation as the outcome and disease duration, age, and sex as the independent variables in addition to their mutual interaction terms. Model selection technique will be adopted to select the optimal parsimonial model deemed for the data. We will also perform subgroup analysis to

compare the slope magnitude estimation between PD patients with PAS (penetration-aspiration scale) no more than 2 and PD patients with PAS greater than 2 by adjusting confounding factors of age, gender and BMI, etc. to demonstrate that reduced slope of magnitude estimation is present in PD patients regardless of PAS status. We will include other swallow and cough outcome variables in this model to determine relationships between dependent variables.

**Aims 2 and 3:** We will first fit a multiple regression model with P1 and N2 peak amplitude and gating ratios as the dependent variable and condition (1 = attend and 2 = ignore) as independent variables by controlling confounding variables including age, gender, BMI, etc. In order to determine the relationship between P1 and N2 peaks and swallow and cough function, we will fit a second multiple regression model with P1 and N2 (amplitude and gating ratio), cough and swallow outcomes as the dependent variables and disease duration as the primary independent variable by controlling confounding variables including age, gender, BMI, etc. Also, model selection technique will be adopted to select the optimal model. Besides the primary outcomes of P1 and N2 peaks, other secondary outcomes such as N1 and P2 amplitudes and gating ratios will be analyzed.

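### Protocol 1 plans 30 healthy controls, but no Aims 1-3 analysis uses them, so the PD-only comparison by PAS cannot show a slope that is reduced regardless of PAS status

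*Combined protocol and SAP*

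**What the plan says.** The opening of Protocol 1 (section 6) describes men and women with PD, "as well as a control group consisting of healthy adults. We aim to recruit 30 participants in each group". Its Statistical Analysis section then sets out four analyses for Aims 1-3:

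- **Aim 1 regression:** "the slope magnitude estimation as the outcome and disease duration, age, and sex as the independent variables", plus interactions and model selection.
- **Aim 1 subgroup analysis:** PD with PAS no more than 2 against PD with PAS above 2, adjusted for age, gender, BMI and similar factors. The stated purpose is "to demonstrate that reduced slope of magnitude estimation is present in PD patients regardless of PAS status".
- **Aims 2 and 3, first model:** P1 and N2 amplitude and gating ratios, with "condition (1 = attend and 2 = ignore) as independent variables by controlling confounding variables including age, gender, BMI, etc".
- **Aims 2 and 3, second model:** P1, N2, cough and swallow outcomes, with "disease duration as the primary independent variable by controlling confounding variables including age, gender, BMI, etc", again followed by model selection.

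Hypothesis 2 (section 5) opens by predicting that discriminative processing is reduced in people with PD. The Background links the P1 peak to that kind of processing.

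**The concern.** Words such as reduced and blunted describe a departure from normal. The Background uses them that way. Its load study reports "blunted magnitude estimation of inspiratory resistive loads as compared with the control group regardless of whether they exhibit measurable decline in swallowing safety". Its evoked-potential work describes changes "in people with PD as compared to an age- and sex-matched control group", and specifically changes to "both P1 (discriminative) and N2 (affective) peaks as compared to healthy older adults (Table 4"). The planned analyses drop the comparison on which those statements rested.

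If the plan is followed as written, the Aim 1 conclusion on PAS status will be unsupported whatever the data show, and the first clause of Hypothesis 2 will go untested although control data are planned. A control comparison added once the data are known would be post hoc, with a free choice among peaks, among amplitude and gating ratio, and between attend and ignore conditions.

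**Working it through.** **Inputs.** The documents give 30 per group for Protocol 1, with no effect size, SD, alpha or power behind it, so there is no figure to reproduce. The only power calculation is for Protocol 2 and does not enter here. The rest is assumed: two-sided alpha 0.05, effects in SD units with a common SD, PAS splits of 15/15 or 20/10 among the 30 with PD, and no covariate adjustment.

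**Step 1: which analysis has a control reference?** The key predictors are disease duration, PAS subgroup within PD, attend/ignore condition, and disease duration again. None separates PD from control.

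**Step 2: what can the PAS comparison show?** Let the mean slopes be C (controls), L (PD, PAS 2 or less) and H (PD, PAS above 2). The intended claim is L < C and H < C. The planned contrast estimates L − H, which does not contain C.

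- If L and H differ, one of them may still equal C.
- If L and H do not differ, both may equal C.

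A simulation (20,000 runs, 15/15 split, L = H) shows this:

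| True state | PAS contrast non-significant | 30 v 30 PD-control test significant |
|---|---|---|
| PD 1 SD below controls | 95.2% | 96.8% |
| PD equal to controls | 95.2% | 4.9% |

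The planned contrast behaves the same in both states. The omitted comparison tells them apart.

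**Step 3: would no difference at least show similarity?** Only weakly. Power of the PAS contrast at 0.5 SD is 26% (15/15) or 24% (20/10); at 0.8 SD it is 56% or 51%. The 95% CI half-width is t(28 df) × √(1/n₁ + 1/n₂):

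- 15/15: 2.048 × √(1/15 + 1/15) = 0.75 SD
- 20/10: 2.048 × √(1/20 + 1/10) = 0.79 SD

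**Step 4: what would a control comparison deliver?** For one contrast the noncentrality is d × √(n₁n₂/(n₁+n₂)).

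- All PD against controls, 30 v 30, d = 0.8: 0.8 × √15 = 3.10, power 0.86.
- 15 PD v 30 controls, d = 0.8: 0.8 × √10 = 2.53, power 0.70.
- 10 PD v 30 controls, d = 0.8: 0.8 × √7.5 = 2.19, power 0.57.
- 20 PD v 30 controls, d = 0.8: 0.8 × √12 = 2.77, power 0.78.

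The claim needs both PD subgroups to be reduced. With a shared control group, pooled error on 57 df, the same true effect in both subgroups and 1,000,000 simulations, joint power is:

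| PAS split | 0.6 SD | 0.8 SD | 1.0 SD | 1.2 SD |
|---|---|---|---|---|
| 15/15 | 0.27 | 0.54 | 0.78 | 0.93 |
| 20/10 | 0.25 | 0.49 | 0.73 | 0.89 |

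The rule would claim wrongly about 0.3% of the time if neither subgroup is reduced, and at most 2.5% if only one is. No alpha adjustment is needed because both contrasts must succeed.

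**The case against.** The strongest reply is that Aims 1-3 are worded as relationships within people with PD. None asks for a PD-control comparison, and the PAS analysis is an addition to the main Aim 1 regression. This stands as a limit on scope: the within-PD duration and association analyses can go ahead as planned. It does not rescue a conclusion that the plan itself attaches to the PAS comparison.

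Three readings might supply the missing reference, but none does. The open-ended adjustment list refers to confounders, not to a group contrast. Disease duration is undefined for controls; coding it as zero is not stated and would mix group with duration. Nothing says that the pilot controls are to serve as the reference.

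A reader might also go further than the documents allow:

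- **That Hypothesis 1 as a whole is untested for want of controls.** It is mainly a claim about order, with blunting before cough or swallowing dysfunction. Early blunting is one part of it, and a cross-sectional control comparison could not establish sequence.
- **That ignoring the pairing of attend and ignore recordings makes the plan's SEP tests too liberal for a group effect.** The plan has no group term, so such inflation is not a fault of the plan as written. The pairing matters for how a group term is added.
- **That Table 4 supplies an effect size for P1.** The table does not say whether its values are amplitudes or gating ratios. The accompanying text speaks of over-filtering, which suggests ratios, so power for a chosen P1 measure cannot be taken from it.

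**Conclusion.** The point holds. As written, no Aims 1-3 analysis uses the 30 planned controls. The Aim 1 conclusion on PAS status cannot be supported by its named analysis whichever way the result falls, and the first clause of Hypothesis 2 has no test against normal. This follows from the model terms alone.

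The power figures describe the repair, not the defect, and rest on assumed effects and PAS splits. Under those assumptions the joint claim is well supported only for effects of about 1 SD or more. The documents do not support the wider inference that Aims 1-3 fail: their within-PD association questions are untouched.

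**What to change.** Amend the Protocol 1 Statistical Analysis section before any data are analysed:

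1. **Aim 1.** State that the disease-duration regression is PD-only. Add a magnitude-estimation model on all 60 planned participants with a three-level group factor (control; PD, PAS 2 or less; PD, PAS above 2), adjusted for age, sex and BMI. State that controls form one reference group whatever their own PAS, since the procedure list does not exempt them from fluoroscopy. Claim a reduced slope regardless of PAS status only if both PD-control contrasts show reduction. Report the between-PAS difference with a 95% CI. State two limitations: joint power is good only for large effects, and PAS status is not separated from disease duration.
2. **Aims 2 and 3.** Add a PD-versus-control term and its interaction with condition to the first (attend/ignore) SEP model, with a participant random effect because each person contributes both conditions. Name in advance the P1 measure, amplitude or gating ratio, that tests the opening clause of Hypothesis 2. Keep the duration-based SEP model PD-only.
3. **Model selection.** State that the group factor, the group term and the group-by-condition interaction are fixed in these models. Otherwise selection could drop or merge them, and the joint power and error rates would no longer apply.
4. **Optional.** Report PD at 0-5 years against controls, with CIs, for sensation, cough and swallowing outcomes, labelled as descriptive only.

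Cost: no new data. The change is text, plus a mixed model in place of ordinary regression for the first SEP analysis.

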diagnosis, blunted respiratory somatosensation will correlate with reduced reflexive cough sensitivity and effectiveness, and decline in swallow function and safety (Figure 1). We will determine airway somatosensitivity using resistive inspiratory loads (8). We will perform fluoroscopic studies to evaluate swallowing function, and reflex cough testing using capsaicin to determine sensitivity and effectiveness. We will perform these tests in people across a range of disease durations. The rationale is that by determining the general respiratory sensitivity, reflex cough sensitivity to an airway irritant (capsaicin), as well as swallowing and cough effectiveness, we will be able to identify whether the onset of swallowing and/or cough deficits occur after reduced respiratory somatosensation. These data will provide support to our hypothesis that reduced respiratory somatosensation underlies observable motor deficits in swallowing and cough function, as well as reduced reflex cough sensitivity. This will significantly advance our understanding of the perceptual sensory components of airway protective deficits in PD, and provide much needed information regarding why airway protection deficits develop. Such outcomes are critically important to advancing the management of patients with PD and other neurodegenerative diseases.

[figure not shown]

Figure 1. Hypothesized relationship between airway protective behaviors and airway somatosensation with Parkinson's disease duration. PAS is penetration-aspiration score; dtLVC\_H1 is duration from initial hyoid burst (H1) to laryngeal vestibule closure (LVC), UtC is urge to cough.

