## **5. Specific Aims:**

The specific aims for this project are:

Aim 1: To determine the relationships between blunted airway somatosensation, reflex cough sensitivity and effectiveness, and swallowing function in people with PD.

Hypothesis 1: We predict that blunted airway somatosensation will appear earlier (years 0 – 5 post-diagnosis) in the disease process than either cough or swallowing dysfunction, and that by 6-10 years post-diagnosis, blunted respiratory somatosensation will correlate with reduced reflexive cough sensitivity and effectiveness, and decline in swallow function and safety.

Specific aim 2: To determine whether measures of discriminative and affective processing of general airway sensation is/are associated with deficits in reflex cough and swallowing function in people with PD.

Hypothesis 2: People with PD will exhibit reduced discriminative processing components of airway stimuli. With disease progression, measures of affective processing components will decline and this will directly correlate with diminished reflex cough sensitivity and swallowing function.

Specific aim 3: To determine whether over-filtering of airway stimuli is associated with swallowing or cough deficits in people with PD.

Hypothesis 3: Over-filtering of airway stimuli will be associated with deficits in reflex cough and swallowing function in people with PD.

Aim 4: Determine the relationships between observable motor aspects of swallowing, cough, and cough sensitivity over a 3-year time period in people with PD.

Hypothesis 4: Swallowing safety and physiology in people with PD will exhibit significant differences over 3 time points, spaced 10 – 18 months apart. For people within 9 years of PD diagnosis, reduced reflex cough sensitivity will not be a sensitive and/or specific indicator of swallowing dysfunction. However, for those with a greater disease duration (10+ years), reflex cough sensitivity will be a sensitive and specific biomarker of swallowing dysfunction.

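### Aim 1 puts cough and swallow measures into a model for airway sensation, so on the natural reading its coefficients do not estimate the separate links that Hypothesis 1 predicts

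*Combined protocol and SAP*

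**What the plan says.** All of this is in the combined protocol and SAP.

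- **Aim (section 5):** "To determine the relationships between blunted airway somatosensation, reflex cough sensitivity and effectiveness, and swallowing function in people with PD".
- **Hypothesis 1 (section 5):** by 6-10 years after diagnosis, "blunted respiratory somatosensation will correlate with reduced reflexive cough sensitivity and effectiveness, and decline in swallow function and safety".
- **Causal idea (section 4, airway somatosensation):** the data are expected to support the hypothesis that "reduced respiratory somatosensation underlies observable motor deficits in swallowing and cough function".
- **Model (section 6, Protocol 1, under Aim 1 of the Statistical Analysis):** the paragraph opens with "A multiple regression analysis will be conducted with the slope magnitude estimation as the outcome and disease duration, age, and sex as the independent variables", with their interactions. Then: "Model selection technique will be adopted to select the optimal parsimonial model deemed for the data".
- **Subgroup comparison (same paragraph):** slope in PD participants with PAS up to 2 against PAS above 2, "to demonstrate that reduced slope of magnitude estimation is present in PD patients regardless of PAS status".
- **Cough and swallow measures (last sentence of that paragraph):** "We will include other swallow and cough outcome variables in this model to determine relationships between dependent variables".

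No other Aim 1 analysis is given. In particular, none takes the cough or swallow measures one at a time.

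**The concern.** Hypothesis 1 is a set of separate associations: sensation with reflex cough sensitivity, with cough effectiveness, and with swallowing. The last sentence for Aim 1 is the only place where the plan addresses them together, and it adds the measures to a model that already has sensation as its outcome. If they enter jointly, the C2 coefficient is the link between C2 and sensation with PAS, peak flow, timing and the rest held fixed. On the protocol's own account these are parallel consequences of one sensory deficit, so each takes part of the signal that another should show.

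Reversing outcome and predictor would not by itself matter: in a linear model with one measure and the same covariates, the test is the same either way. Joint entry is what changes the estimate. The problem is present even if no model selection is done.

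At stake is whether Aim 1 can say which airway-protective function is related to sensation.

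**Working it through.** **Inputs from the documents.** Protocol 1 aims for 30 participants per group. Disease duration is undefined for controls, so I take the model as PD-only, n = 30; the plan does not say so. The procedure sections list 16 measures: C2, urge-to-cough, four airflow measures for each of reflex and voluntary cough (8), PAS, and five swallow timings. Cough volume acceleration is defined as peak flow divided by rise time, so it is computed from two other listed measures.

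**Inputs not in the documents.** These are r, the correlation of sensation with each measure, and ρ, the correlation between measures. I assume r = 0.3 and 0.5. The r = 0.40 cited in the background relates laryngeal threshold to disease severity and does not supply r. If sensation is the only thing the measures share, ρ = r². Aim 1 states no power or effect size, so there is no planned figure to reproduce.

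**Coefficient under joint entry.** For k measures with equal correlations, the standardised coefficient is r / (1 + (k − 1)ρ). With ρ = r²:
- r = 0.5, k = 5: 0.5 / (1 + 4 × 0.25) = 0.25
- r = 0.5, k = 12: 0.5 / (1 + 11 × 0.25) = 0.13
- r = 0.3, k = 5: 0.3 / (1 + 4 × 0.09) = 0.22
- r = 0.3, k = 12: 0.3 / (1 + 11 × 0.09) = 0.15

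If the measures are more alike than that (ρ = 0.5, k = 12), the values are 0.5 / 6.5 = 0.077 and 0.3 / 6.5 = 0.046.

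**Power for one given measure.** Simulated least-squares t-tests at two-sided 5%, n = 30, three covariates, ρ = r². Repeat runs differ in the second decimal.

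| Assumed r | Alone | 5 measures | 12 measures |
|---|---|---|---|
| 0.5 | 0.79 | 0.39 | 0.15 |
| 0.3 | 0.32 | 0.23 | 0.13 |

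**What is kept.** The explained variance is k × r × coefficient. At r = 0.5 it rises from 0.25 with one measure to 12 × 0.5 × 0.133 = 0.80 with twelve. In the r = 0.5 simulations an F-test of the whole block has power 0.94 or more, and at least one coefficient is significant in 80-93% of runs with three covariates.

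**Other correlation patterns.** Take two measures with r₁ = 0.5, r₂ = 0.1 and ρ = 0.6. The joint coefficients are (0.5 − 0.6 × 0.1) / (1 − 0.36) = 0.69 and (0.1 − 0.6 × 0.5) / (1 − 0.36) = −0.31. One is inflated and the other changes sign.

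**Upper limit on model size.** Duration, age and sex with all interactions give 3 + 3 + 1 = 7 terms. Adding 16 measures and an intercept gives 24 parameters, leaving 30 − 24 = 6 residual degrees of freedom. This is the extreme case, with every term kept.

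**The case against.** **The text does not say that all measures enter, or that they enter together.** That stands. A reader might infer a single model holding every listed measure, but the sentence does not say so, the planned selection could drop some, and it is unclear whether the model meant is the main regression or the PAS comparison just before it. The 6 residual degrees of freedom are therefore a limit, not the plan. Selection would not cure the problem, however: any two or more measures that remain are still adjusted for each other.

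**The measures may be meant as outcomes.** The sentence calls them dependent variables, and the Aims 2 and 3 paragraph does treat cough and swallow measures as dependent variables with disease duration as the main predictor. On that reading nothing is mutually adjusted and no attenuation arises. But each measure would then be regressed on duration, age and sex, and its link with the load slope would not be estimated at all. Aim 1 is missed either way.

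**The study would not simply come out null.** A reader might infer that it would conclude sensation is unrelated to airway protection. The figures do not support that: at r = 0.5 the block test nearly always detects something. With three covariates, no coefficient is significant in about 7-20% of runs, no more often than a one-measure model misses its single link (about 21%). With 15 measures and 7 covariates, at least one is still significant in about 56% of runs.

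**Attenuation is conditional.** That also stands. It rests on assumed correlations and the common-cause structure. Equal r for PAS also sits awkwardly with the expectation that blunting is present whatever the PAS status, although Hypothesis 1 does predict a correlation with swallow safety later in the disease.

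**Conclusion.** The point holds in a limited form. On the natural reading, Aim 1 yields mutually adjusted coefficients, which are not the separate relationships in Hypothesis 1. Under the protocol's own hypothesis they would be attenuated: at an assumed r = 0.5 the coefficient for a given measure falls by half with 5 measures and by about 73% with 12. Under other patterns they could be inflated or reversed. Power for one measure is modest at r = 0.3 even when it is analysed alone, so joint entry worsens a limit already set by n = 30.

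The loss is mainly of attribution to a named cough or swallow function. The block-test reassurance is shown only for r = 0.5, and such a test cannot separate cough from swallowing, as Aim 1 requires. The sizes rest on assumed equal correlations, a PD-only model and 30 participants. The mismatch between coefficient and hypothesis does not depend on those values. The sentence should be corrected before analysis.

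**What to change.** Replace the last sentence of the Aim 1 analysis with wording such as:

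> For each cough and swallow outcome in turn, a regression will be fitted in PD participants with that outcome as dependent variable and the load slope as predictor, adjusting for prespecified disease duration, age and sex, using a model suited to the outcome's scale (for example ordinal for PAS and C2). The load-slope coefficient will be reported with its 95% confidence interval. A load slope by disease duration term will then be added to address the 6-10 year prediction. PAS and C2 are the two main outcomes; the others are exploratory. No cough or swallow outcome will be adjusted for another.

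This needs no new data. The costs are several small models instead of one, secondary results that must be labelled exploratory because of multiplicity, and an interaction that will be estimated imprecisely with 30 participants. If the sponsor also wants a joint model, it can be kept as a descriptive supplement with its block test, stating that its coefficients are mutually adjusted.
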